#### 4. OBJECTIVES\*

a) Primary objective: To determine if pre-operative fiber intake reduces time to first bowel movement after surgery.

b) Secondary objective: To evaluate if pre-operative fiber intake reduces pain associated with first bowel movement after surgery.

#### 5. BACKGROUND\*

Post-operative constipation is a well-known concern among patients undergoing pelvic reconstructive surgery. A retrospective study reviewing all patient-initiated telephone calls in the postoperative period after pelvic reconstructive surgery found the most frequent concern among patients to be constipation (Ramaseshan, 2018). There are various strategies for managing post operative constipation but few of these are evidence-based. Strategies typically involve stool softeners, laxatives, stool bulking agents or a combination of these medications.

The current evidence has focused on postoperative medications to improve time to first bowel movement. A study by Patel et al. (2010) found that senna-docusate decreases time to first bowel movement postoperatively when compared to placebo in patients undergoing pelvic reconstructive surgery. Another study examined the effect of a standardized post-operative bowel regimen of over-the-counter medications including docusate, Miralax, fiber wafers and Bisacodyl suppositories and found minimal differences between the combination of medications compared to docusate alone (McNanley, 2012).

There has been an increased attention placed on fiber-containing regimens for perioperative bowel management. It is well-documented that the Western diet is low in fiber and most adult women do not meet the recommended consumption of 25g of fiber per day. Moreover, women with pelvic organ prolapse are at higher risk for constipation than controls. One study suggested that this increased risk could partially be explained by lower intake of dietary insoluble fiber in women with prolapse when compared to controls (Arya et al., 2005).

An alternative approach to postoperative constipation involves consideration of the preoperative period. There is an increasing interest in preoperative optimization and preparation for surgery. There is limited information regarding the effect of preoperative therapies and their effect on postoperative constipation. One study examined the effect of pre-operative mechanical bowel preparation on postoperative return to bowel function and found no difference between the intervention and control group (Ballard et al., 2015). However, mechanical bowel preparation is no longer recommended prior to benign gynecologic surgery. Thus far, there have been no studies examining the use of pre-operative fiber supplementation prior to pelvic reconstructive surgery to improve time to first bowel movement after surgery and pain associated with first bowel movement. Fiber may be of benefit as it appears to have a regulating effect on bowel movements.

#### 6. INCLUSION AND EXCLUSION CRITERIA\*

Inclusion criteria:

- Women undergoing prolapse repair with or without hysterectomy on the UMass urogynecology service

Exclusion criteria:

- Unable to provide consent
- Under 18 years of age
- Pregnant women
- Prisoners
- As our validated questionnaires are only available in English, we are unable to offer study participation to Non-English speaking subjects
- Because these conditions intrinsically affect bowel function, women with the following

will be excluded: history of inflammatory bowel disease, colorectal cancer, rectovaginal fistula, sigmoid resection or rectal surgery

- Because the use of motility agents can affect bowel function and stool transit, somen using motility agents such as linaclotide will be excluded.
- Concurrent bowel surgery due to potential effect on the surgical field

- Concurrent anal sphincteroplasty due to potential effect on the surgical field -Insulin-dependent diabetes mellitus with known gastroparesis as this would affect transit of fiber supplement

- Patients with a history of phenylketonuria as the psyllium fiber supplement we will be using contains phenylalanine
- History of placement of sacral neuromodulating device for indication of fecal incontinence, as this would affect bowel function

### 7. Study-Wide Number of Subjects\*

N/A

# 8. Study-Wide Recruitment Methods\* N/A

#### 9. STUDY TIMELINES\*

Subjects will be enrolled from one week before their surgery until 6 weeks after surgery.

Our urogynecology department had approximately 90 postoperative admissions over 12 months (from October 2017 to October 2018). Given this trend, we anticipate approximately 20-24 months to recruit 84 patients.

Primary analysis will be completed within 6 months after enrollment is completed.

#### **10. Study Endpoints\***

The primary outcome is the time to first bowel movement among those who receive preoperative fiber supplementation and those who do not.

The secondary outcome is pain associated with first bowel movement.

We also plan to perform an interval analysis after 50% of subjects have completed their surgery to evaluate postoperative bowel function. If a statistically significant difference (p<0.01) is found on this analysis, we will terminate the study.

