#### **Postoperative care:**

Subjects will undergo routine postoperative care as inpatients and outpatients and have routine follow-up, including a postoperative evaluation at 2 and 6 weeks. Information on any postoperative complications will also be collected, such as severe constipation, infection, urinary tract infection. During our routine 1 week follow up phone call that all patients get, data regarding the primary outcome will be collected. At their 2 week postoperative visit, they will be asked to fill out a validated questionnaire regarding bowel function.

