#### Administration of bowel function-related surveys:

- 1. Validated questionnaires related to bowel function and pain scores will be administered at two time points:
  - (a) At the patient's preoperative visit
  - (b) At their routine 2 week postoperative visit, they will submit their 5-day bowel diary. The primary outcome measures will also be gathered via telephone call to occur 1 week after surgery. At this visit, they will also complete a validated questionnaire regarding bowel function.

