#### 14. PROVISIONS TO MONITOR THE DATA TO ENSURE THE SAFETY OF SUBJECTS\*

Psyllium fiber is a natural-occurring dietary supplement that is available over the counter and is commonly used across millions of individuals in the United States. It comes in insoluble and soluble forms, both of which are important for a balanced diet. We plan to use psyllium in a powdered form, which contains 70% soluble fiber and 30% insoluble fiber. The normal recommended dose for fiber in the form of powdered psyllium is 1 teaspoon up to three times daily. We plan to prescribe 1 teaspoon twice daily in the form of powdered, pre-measured packets that are to be mixed with 8 oz of water or other cool liquid. We will obtain the psyllium fiber through wholesale distribution that has been determined by the investigational drug pharmacy. Receipt, storage, preparation, accountability, dispensing and return/destruction of all study drug will be performed by the Investigational Drug Service (IDS) at the Memorial Campus Inpatient Pharmacy. The Investigational pharmacy has been contacted regarding this study and has received the study protocol and package insert.

The IDS will verify that study drugs supplies are received intact, at the appropriate temperatures, and in the correct amounts from the study drug supplier.

Study drug will be dispensed only by prescription. Research staff will transfer the prepared study medication from the pharmacy to the Urogynecology clinic on West 4th floor of UMass Memorial to give to the subject. The study drug will not be used for reasons other than that described in the protocol. Attached to this protocol is an informational sheet regarding fiber supplementation.

Psyllium fiber supplement is generally well tolerated. It can cause bloating and abdominal discomfort. Subjects will be advised to stop the fiber if they develop symptoms such as abdominal pain, nausea or vomiting. All subjects will have access to our office and an on-call physician should any medication side effects or adverse reactions develop.

If any adverse event were to arise, they would be evaluated by the on-call physician.

We will do an interval analysis of the primary outcome once 50% of subjects have completed the

study. If a statistically significant difference (p<0.01) is found in favor of psyllium fiber supplementation, we will terminate the study and offer preoperative psyllium fiber supplementation to all our patients.

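### Sections 10 and 14 give different rules for the same p<0.01 stopping interim, and no final significance level is matched to it

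*Combined protocol and SAP*

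**What the plan says.** Section 10 (Study Endpoints) sets the interim as follows: "We also plan to perform an interval analysis after 50% of subjects have completed their surgery to evaluate postoperative bowel function". It continues: "If a statistically significant difference (p<0.01) is found on this analysis, we will terminate the study". No direction is given.

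Section 14 (safety monitoring) describes it again: "We will do an interval analysis of the primary outcome once 50% of subjects have completed the" study. The trial stops if a p<0.01 difference is "found in favor of psyllium fiber supplementation, we will terminate the study and offer preoperative psyllium fiber supplementation to all our patients".

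Three other places bear on what these sentences mean:

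- Section 11, Postoperative care, on the primary outcome: "During our routine 1 week follow up phone call that all patients get, data regarding the primary outcome will be collected". On the questionnaire: "At their 2 week postoperative visit, they will be asked to fill out a validated questionnaire regarding bowel function".
- Section 11, on the surveys: "At their routine 2 week postoperative visit, they will submit their 5-day bowel diary".
- Section 9: "Subjects will be enrolled from one week before their surgery until 6 weeks after surgery".

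Section 13 gives a 5% significance level and 80% power as inputs to the sample size (35 per arm, 70 in total, 84 recruited) and names Student's t-test for continuous measures. It does not mention the interim, the sidedness of any test, or the level for the final analysis.

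**The concern.** A rule that can end a trial has to be fixed before the data are seen. Here two written rules cover one analysis. They differ in when it happens, what is tested and which results stop the trial. Patients and providers are unblinded (section 11), and the supplied text describes no independent monitoring board. The choice between the two readings could therefore be made with the interim result in hand.

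The second issue is the significance level. A look at p<0.01 that can stop the trial uses part of the type I error. If the final analysis is then run at the full 5%, the overall error rate exceeds 5%. The plan does not say whether this was intended or allowed for.

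**Working it through.** **Step 1. The two descriptions side by side**

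| Element | Section 10 | Section 14 |
|---|---|---|
| Trigger | Half have had surgery | Half have finished the study (not defined) |
| Outcome | Postoperative bowel function | Primary outcome |
| Result that stops | Any difference, p<0.01 | p<0.01 favoring psyllium |
| p<0.01 against psyllium | Stops | No rule given |

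Finishing the study could mean the 1-week call, the 2-week visit or the 6-week end of participation.

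**Step 2. Size of the trigger gap**

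Sections 9 and 24 expect 84 subjects in 20 to 24 months. Per week, 84/(24 × 52/12) = 0.81 and 84/(20 × 52/12) = 0.97. The two triggers are then separated by:

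- 1 week: 0.8 to 1.0 subjects
- 2 weeks: 1.6 to 1.9 subjects
- 6 weeks: 4.8 to 5.8 subjects

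**Step 3. How often the direction matters**

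Half of the 84 recruited is 42. With the plan's retention of 70/84, 42 × 70/84 = 35 of 70 outcomes, so the information fraction is t = 0.5. A two-sided p<0.01 needs |Z| > 2.576. The effect that gives 80% power at two-sided 5% has an expected final Z of 1.960 + 0.842 = 2.80, or 2.80 × √0.5 = 1.98 at the interim. The chance of crossing against psyllium is:

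- No effect: P(Z > 2.576) = 0.005
- Delay of half that effect: P(Z > 2.576 − 1.40 × 0.707) = 0.056
- Delay of the full effect: P(Z > 2.576 − 2.80 × 0.707) = 0.276

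**Step 4. Overall type I error if the final test is at 0.05**

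The interim and final statistics Z1 and Z2 are treated as bivariate normal with correlation √t.

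- Either direction stops: 1 − P(|Z1| < 2.576, |Z2| < 1.960)
- Only benefit stops, final test two-sided: 1 − P(Z1 < 2.576, |Z2| < 1.960)
- Both tests one-sided for psyllium: 1 − P(Z1 < 2.326, Z2 < 1.645)

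| Rule | Overall error, t = 0.5 | Overall error, t = 0.6 | Final level that holds 5% (t = 0.5) |
|---|---|---|---|
| Two-sided, either direction stops | 0.0546 | 0.0534 | 0.0452 |
| Two-sided, only benefit stops | 0.0523 | 0.0517 | 0.0477 |
| One-sided | 0.0538 | not needed here | 0.0460 |

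The t = 0.6 column is the case in which none of the first 42 subjects drops out (42/70).

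A t-test simulation (1,000,000 null trials, 18 per arm at the interim and 35 per arm at the end) gave 0.0545 and 0.0521 for the two two-sided rules. At the adjusted final levels it gave 0.0498 for both.

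**Step 5. Power after matching the final level**

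Using the effect that gives 80% power in a single-look trial, at t = 0.5, the overall power moves as follows:

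- Two-sided, either direction: 80.4% to 79.2%
- Two-sided, benefit only: 80.4% to 79.8%
- One-sided: 80.4% to 79.3%

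The 35 per arm itself cannot be reproduced, because the plan gives no standard deviation or event proportions. The results above need only the 80% power that the plan claims.

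**The case against.** The strongest reply is that the sections can be read together: section 10 states the general rule, and section 14 says what follows if psyllium wins, since offering psyllium to all patients makes sense only then. Section 14 neither says that only benefit stops the trial nor that an adverse result lets it continue. This is fair as far as it goes: on direction, section 14 is silent and does not flatly contradict section 10. But it is the section on monitoring safety, it restates the stopping rule in narrower terms, and it also changes the trigger. A reader cannot tell which version governs.

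On the outcome, section 10 may simply be loose wording. It defines the primary outcome a few lines earlier, and section 14 names it. That is plausible, but section 11 uses the same phrase, bowel function, for the 2-week questionnaire, so the wording does not identify one measure. This is the weakest of the three differences.

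On the trigger, 6 weeks is a natural reading of finishing the study, and the gap is at most about six subjects. No effect on error rates follows from it.

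On size, nothing in the documents suggests that psyllium delays bowel movement, so the 6% and 28% figures describe a case that the investigators do not expect. The type I excess is 0.2 to 0.5 percentage points and depends on an assumed final test. Both points stand and limit the weight of the concern. They do not remove the need for a single rule.

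**Conclusion.** The concern holds and should be fixed. The trial has two unreconciled versions of a rule that can end it. The difference that matters most is direction: a p<0.01 result against psyllium stops the trial under section 10 and is not covered by section 14. The trigger and outcome differences are smaller.

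The type I error part is minor and conditional. It assumes a final test at 0.05 and about 50% information. With a two-sided final test, the missing adjustment changes the conclusion only for a final p between about 0.045 and 0.05 (either direction stops) or 0.048 and 0.05 (only benefit stops).

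That no final level is stated applies to the supplied text, from which some pages were removed.

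**What to change.** Put one rule, in identical words, in sections 10 and 14. It should:

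- name time to first bowel movement as the outcome tested;
- set the trigger as a stated number of subjects with that outcome recorded;
- state which direction or directions stop the trial. The two sections must be reconciled on this; the choice belongs to the investigators.

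In section 13, state whether the tests are one- or two-sided, and give a final level matched to the chosen rule. At 50% information this is about 0.045 (two-sided, either direction stops), 0.048 (two-sided, only benefit stops) or 0.046 (one-sided). If the trigger falls at a different information fraction, the level should be recomputed.

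The cost is protocol wording and a loss of about 0.6 to 1.2 points of power, by the differences in the power figures above.

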#### **11. PROCEDURES INVOLVED\***

#### Study design and randomization

This study is a randomized trial. We were unable to find a suitable placebo that had the same properties as the psyllium fiber supplementation, and thus we will compare psyllium fiber supplementation to our standard of care, which is no bowel regimen before surgery. Both groups will receive the routine postoperative bowel regimen offered to all patients on the urogynecology service.

Subjects will be screened for eligibility using inclusion and exclusion criteria in our urogynecology clinic after prolapse surgery has been scheduled. Once a patient provides informed consent for the surgical procedure, she will be invited to participate in this study. Once the subject has consented to participate in the study, baseline data will be gathered. Study assignment will be revealed using sequentially numbered sealed opaque envelopes. Randomization will be performed using software and a block randomization scheme to yield a 50% chance of receiving the preoperative fiber supplementation. Those assigned to the intervention group will receive a 7-day supply of fiber supplementation to be taken before surgery. The fiber will be procured, distributed and managed by the investigational drug pharmacy.

Neither the patient nor the provider will be blinded to the allocation of groups. However, our statistician will be blinded to allocation for the data analysis

Psyllium fiber is a commonly used and naturally occurring dietary supplement that is FDA-approved. It is available over-the-counter.

#### Surgery:

On the day of surgery, we will collect information from the patient about their last bowel movement as well as if they were able to adhere to the fiber regimen, had they been allocated to that group. Prolapse surgery will be performed in the usual manner. There will be no changes to the surgical technique for the purposes of the study.

Subjects will receive routine perioperative and postoperative care for their scheduled surgery. The study intervention will require postoperative data collection including the gathering of PHI, a 5-day bowel diary and recording of post-operative medications.

#### **Postoperative care:**

Subjects will undergo routine postoperative care as inpatients and outpatients and have routine follow-up, including a postoperative evaluation at 2 and 6 weeks. Information on any postoperative complications will also be collected, such as severe constipation, infection, urinary tract infection. During our routine 1 week follow up phone call that all patients get, data regarding the primary outcome will be collected. At their 2 week postoperative visit, they will be asked to fill out a validated questionnaire regarding bowel function.

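### Fiber is taken only in the week before surgery, but no planned question asks about symptoms in that week or why women stopped

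*Combined protocol and SAP*

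**What the plan says.** Dosing is entirely preoperative. Section 11 (Study design and randomization) states: "Those assigned to the intervention group will receive a 7-day supply of fiber supplementation to be taken before surgery". Section 14 sets the dose at one pre-measured packet twice a day. The control arm gets nothing before surgery: "thus we will compare psyllium fiber supplementation to our standard of care, which is no bowel regimen before surgery".

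On the day of surgery, section 11 (Surgery) collects the last bowel movement "as well as if they were able to adhere to the fiber regimen, had they been allocated to that group". After surgery, the plan collects a 5-day bowel diary and medications (Surgery), data for the primary outcome at a one-week call, a bowel-function questionnaire at two weeks, and complications: "Information on any postoperative complications will also be collected, such as severe constipation, infection, urinary tract infection" (Postoperative care). For the questionnaires, section 11 says: "Validated questionnaires related to bowel function and pain scores will be administered at two time points". These are the preoperative visit and the two-week visit.

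Section 14 names bloating and abdominal discomfort as effects of psyllium. Section 16 lists cramping, bloating and altered bowel habits as risks. Section 14 also gives a stopping instruction: "Subjects will be advised to stop the fiber if they develop symptoms such as abdominal pain, nausea or vomiting". For side effects it provides the following: "All subjects will have access to our office and an on-call physician should any medication side effects or adverse reactions develop", and "If any adverse event were to arise, they would be evaluated by the on-call physician".

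**The concern.** The exposure and the planned symptom collection do not overlap in time. The protocol names the symptoms it expects from fiber and tells women to stop for some of them, but it describes no step that asks whether those symptoms occurred or whether the instruction was followed, when, and for what reason.

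The practical stake is the decision that follows a positive result. Under section 14, a significant interim difference favoring fiber ends the trial, and preoperative fiber is then offered to all the service's patients. Section 32 describes fiber as already routine for outpatients, so the product is familiar. Use before surgery would nonetheless be new, since the current standard there is no regimen. As described, the team would take that step without a systematic comparison between arms of most of the symptoms the protocol itself names, and without knowing why any woman stopped. Data from the dosing week that are not asked for at the time are hard to recover later.

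**Working it through.** The plan states no figure on this point, so the check sets the dosing period against each contact it describes.

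**Exposure.** 7 days × 2 packets a day = 14 planned doses, all before surgery (sections 11 and 14).

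**Contacts in time order.**

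| Contact | Collected, as described | Asks about the dosing week? |
|---|---|---|
| Preoperative visit (sections 11, 22) | Questionnaire, consent, randomization; baseline data are gathered before assignment is revealed | No, it precedes dosing |
| Day of surgery (section 11, Surgery) | Last bowel movement (both arms); whether the regimen was followed (fiber arm) | Only through these two items |
| Days after surgery (section 11, Surgery) | 5-day bowel diary, postoperative medications | No |
| One-week call (section 11, Postoperative care) | Primary outcome | No |
| Two-week visit (section 11) | Bowel-function questionnaire, diary handed in | Not as described |
| Postoperative follow-up (section 11, Postoperative care) | Postoperative complications | No |
| Office or on-call physician (section 14) | Clinical evaluation if the woman makes contact | Only if she reports it |

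All 14 doses fall between the two questionnaire time points.

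**Symptom coverage.** Combining the effects named in sections 14 and 16 with the reasons to stop in section 14 gives five groups:

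1. bloating: no planned question
2. cramping, discomfort or abdominal pain: no planned question
3. nausea: no planned question
4. vomiting: no planned question
5. change in bowel habit: partly covered by the last bowel movement

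Without a planned question: 5 − 1 = 4.

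Nausea and vomiting appear only as reasons to stop, not as listed effects of fiber. Counting listed effects alone leaves three groups (bloating, cramping or discomfort, bowel habit), of which 3 − 1 = 2 have no planned question. The gap remains on either count.

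**Reason for stopping.** The adherence item is described as whether a woman managed the regimen. Neither the day nor the reason is mentioned. Intolerance is one possible cause of incomplete intake; a short lead time is another. Section 9 starts enrollment one week before surgery, which allows a full course, but section 30 puts the preoperative visit several days beforehand, which may not. With only the adherence item as described, the two causes could not be told apart.

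**The case against.** The strongest reply is that the safety plan fits the risk. Psyllium is sold over the counter, is described as generally well tolerated and is already prescribed routinely by this service (sections 14, 16 and 32). Women are told when to stop and whom to call, and any adverse event is evaluated by a physician. Tolerability is not an objective (section 4). With no placebo and about 35 women per arm, an unblinded symptom table would support little inference. All of this stands, and it is why the point is minor. It does not supply the missing information: section 14 describes clinical care that the patient initiates and does not say that such contacts become study data. A woman with mild bloating who stops need never call.

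Second, other provisions might fill part of the gap. The investigational pharmacy handles accountability and return of the packets (section 14), which could give a dose count. Participants authorize access to their medical records (section 27), so calls might be found there. Neither route asks about symptoms, and a packet count gives neither the day nor the reason for stopping.

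Third, section 11 is a summary, not a data form. The case report forms, the questionnaires and the fiber information sheet were not in the text available, nor was the part between sections 22 and 24. Staff who ask about adherence may well hear and note a reason. This is a fair limit: the finding concerns what the protocol describes, and an item on an unseen form cannot be excluded.

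**Conclusion.** The concern holds as a minor design point. As described, all 14 planned doses are taken in a period for which four of the five symptom groups mentioned (two of three if only listed effects of fiber are counted) have no planned question, and the reason and day of stopping are not planned data. No effect on the primary comparison is claimed. A passive reporting route exists and covers the dosing week.

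The conclusion rests on section 11 being a reasonable description of what is collected at each contact. If the forms already carry these items, one sentence in section 11 saying so would settle the matter.

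**What to change.** At the existing day-of-surgery contact:

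- Ask both arms the same short checklist covering the time since randomization: bloating, cramping or abdominal pain, nausea, vomiting, change in bowel habit. The control arm is needed because background symptoms otherwise cannot be separated from effects of fiber.
- In the fiber arm, extend the adherence question to doses taken, day stopped and reason. Returned packets can support the dose count.
- Tabulate the symptoms by randomized arm, and the adherence and stopping data for the fiber arm, at the interim and final analyses.

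The cost is a few questions at a contact that already takes place, with no extra visit, procedure or change in sample size. The downside is that the answers are unblinded, recalled self-report, so they should be presented descriptively and not tested.

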#### **22.** Setting

Subjects will be identified and recruited in the urogynecology clinic at UMass Memorial on West 4th floor at the time of their pre-operative visit. At this visit, the patients will be consented, and they will also fill out the pre-operative questionnaire. At this time, they will also be randomized

to standard of care versus intervention. The urogynecology division has two full-time designated surgeons (including the PI) and both will participate in the study. In addition, the department fellows and nurse practitioner will work as co-PI and study assistants. This comprises the team who will recruit subjects and obtain intraoperative and postoperative study data.

Data entry and analysis will be performed in the administrative offices of the division on Jaquith 2 in UMass Memorial.

There will be no community advisory board, and this research will not be conducted outside of UMass or its affiliates.

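### Nothing keeps the 1-week caller unaware of arm, and no rule says whether the diary or the call defines time to first bowel movement, so avoidable interviewer bias may enter

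*Combined protocol and SAP*

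**What the plan says.** Section 10 defines the endpoint: "The primary outcome is the time to first bowel movement among those who receive preoperative fiber supplementation and those who do not".

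Section 11 gives two sources for it.

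- **The call.** Under Postoperative care: "During our routine 1 week follow up phone call that all patients get, data regarding the primary outcome will be collected". Under Administration of bowel function-related surveys: "The primary outcome measures will also be gathered via telephone call to occur 1 week after surgery".
- **The diary.** Under Surgery, the required postoperative data include "a 5-day bowel diary and recording of post-operative medications". Under the surveys heading: "At their routine 2 week postoperative visit, they will submit their 5-day bowel diary".

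On masking, section 11 (Study design and randomization) states: "Neither the patient nor the provider will be blinded to the allocation of groups". It adds that the statistician will be masked for the analysis, and explains the open design by the lack of a suitable placebo.

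On staffing, section 22 names two surgeons and says that "the department fellows and nurse practitioner will work as co-PI and study assistants". It continues: "This comprises the team who will recruit subjects and obtain intraoperative and postoperative study data".

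The plan does not say who makes the call, whether that person knows the arm, how the question is put, or which source prevails when diary and call differ.

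**The concern.** The lack of a placebo explains why the woman and her surgeon know the arm. It does not explain why the person who asks for and writes down the outcome should know it. Masking the statistician protects the analysis choices but not the values that reach the analysis.

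A time of first bowel movement given by telephone about a week after surgery is open to prompting, probing and rounding. If the caller knows the arm, these can differ between arms, and the difference goes straight into the comparison of means. The same values also feed the halfway look described in sections 10 and 14, which can stop the trial.

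The diary could largely prevent this, because the woman can record the event when it happens. It does so only if its entry is the analysed value, and the plan does not say that it is.

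**Working it through.** **1. The provisions side by side**

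| Question | What the plan provides |
|---|---|
| Who knows the arm? | Patient and provider (section 11) |
| Who is masked? | The statistician only (section 11) |
| Who obtains postoperative data? | The team that recruits (section 22) |
| Who makes the 1-week call? | Not stated |
| Fixed question or arm-free call sheet? | None described |
| Who enters the data? | The study assistants, monthly (section 26); by section 22 these include fellows and the nurse practitioner |
| Diary or call if they differ? | Not stated |

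The team also asks about adherence to the fiber on the day of surgery (section 11, Surgery), so its members have ordinary occasions to learn the arm before the call. Section 26 stores data under a study number. That protects confidentiality but does not by itself mask the caller or the person entering the data.

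**2. What each source can cover**

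If the diary starts at surgery, it covers 5 × 24 = 120 h. The call comes at about 7 × 24 = 168 h. Section 13 puts the average time near 72 h, so many first movements should fall within the diary window, though the plan gives no distribution. For those women both sources could hold a value. For an event after day 5 or a blank diary, the call is the only stated source. The diary is handed in at 2 weeks, after the call, and the caller is not told to have it read out.

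**3. The plan's own figure**

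The 35 per arm in section 13 cannot be reproduced, because the plan gives neither an SD nor proportions. It cites a chi-squared test for the sample size and a t-test for continuous measures. On a two-sided comparison of means at 5% and 80% power, 35 per arm for a 24 h difference implies

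SD = 24 / [(1.960 + 0.842) × √(2/35)] = 24 / (2.802 × 0.2390) ≈ 35.8 h.

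This is a back-solved value, not the plan's SD, so a range from 24 to 48 h is shown.

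**4. Illustration of what a differential shift would do**

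Assume no true effect, 35 per arm, and recorded times that differ between arms by b hours for reporting reasons alone. Then SE = SD × √(2/35), and the two-sided rejection probability is Φ(b/SE − 1.96) + Φ(−b/SE − 1.96). A value of b = 6 h would arise if half of one arm were shifted by 12 h (0.50 × 12), and b = 3 h if a quarter were (0.25 × 12). These shifts are assumptions. Against the 24 h target they are 6/24 = 25% and 3/24 = 12.5%.

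| SD | SE | b = 3 h | b = 6 h |
|---|---|---|---|
| 24 h | 24 × 0.2390 = 5.74 h | 8.2% | 18.2% |
| 35.8 h | 35.8 × 0.2390 = 8.56 h | 6.4% | 10.8% |
| 48 h | 48 × 0.2390 = 11.47 h | 5.8% | 8.2% |

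For example, at SD 35.8 h and b = 6 h, b/SE = 0.70, and Φ(−1.26) + Φ(−2.66) ≈ 0.104 + 0.004 = 0.108.

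Under a diary-first rule, caller influence would apply only to women whose value comes from the call, so b would shrink in proportion to their share.

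**The case against.** The strongest reply has four parts.

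- **The caller is not identified.** A reader might infer that each woman is telephoned by the person who recruited her and knows her arm. Section 22 makes that plausible, but the call is described as routine follow-up for all patients, and section 24 keeps clinical staff out of recruitment. Someone outside the recruiting team may make it. This stands: the plan leaves masking unassured, but does not show an unmasked caller.
- **The outcome is not taken by telephone alone.** The surveys heading says it is *also* gathered that way, next to the diary. The diary window closes before the call, so many women could answer from it. A reader might call the endpoint purely a recalled time, but the documents do not support that. What remains is the missing precedence rule.
- **Such bias is not beyond repair in the analysis.** A reader might suppose that it is. Using the diary time removes caller influence for every woman with an entry. The answer is to write that rule down before data are seen.
- **The false-positive rates rest on assumptions.** The size of the shift, its single direction and the SD are all assumed. This stands in full. The figures show only that a shift of a few hours would matter at this sample size.

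It is also fair to say that a masked caller leaves the woman's own unmasked reporting untouched.

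**Conclusion.** The point holds as an avoidable risk, not as demonstrated bias. The documents establish an open-label trial, a self-reported primary endpoint gathered at a 1-week call, one team that both recruits and obtains postoperative data, masking of the statistician alone, and no rule giving the diary or the call precedence. They do not establish that the caller knows the arm, or that any bias exists, in which direction, or how large.

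A reader might take 11%, or any other entry in the table, as the trial's actual error rate. The plan supports no such figure. For an assumed 6 h shift the range is about 8% to 18%, depending on an SD that the plan does not give.

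This is a cheap improvement worth making to the primary endpoint. It is not a fatal flaw and does not affect the sample size.

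**What to change.** Amend the two parts of section 11 that describe outcome collection (Postoperative care, and Administration of bowel function-related surveys) as follows.

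1. The analysed time to first bowel movement is the diary entry whenever there is one, entered by someone masked to arm.
2. The 1-week call supplies the value only when the diary has no entry or the event falls after day 5.
3. The call opens with one fixed question, the date and clock time of the first bowel movement, before any other topic. The call sheet does not show the arm.
4. Where feasible, the caller is an existing team or clinic member who did not enrol that woman or hand her the fiber.

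The cost is a short protocol amendment, a call script and some rota planning. The call is already made to every patient, so no extra contact is needed. Some women will reveal their arm during the call, and their own reporting bias remains. The change reduces the interviewer's part of the risk and does not make the endpoint masked.
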